## Inclusion Criteria:

Patients with traumatic brain injury, defined by presence of potential progressive intracranial injury on CT scan imaging, at significant risk for urgent neurosurgical procedure as determined by neurosurgical evaluation, who meet at least one of the following:

- a) History or indication of pre-injury antiplatelet agent use
- b) Need for platelet transfusion per standard practice

Exclusion Criteria:

1. Wearing NO CriSP opt out bracelet
2. Hypotension in ED (SBP< 90 mmHg)
3. Age > 89 or < 18 years of age
4. Penetrating injury
5. Prisoner
6. Pregnancy
7. Going to operating room for non-neurosurgical intervention in first 60 minutes
8. Platelet transfusion contraindicated per care team (for example, recent vascular stent, embolic stroke, intracranial and/or vascular lesions)
9. Objection to study voiced by participant or family member in Emergency Department
10. Currently on therapeutic anticoagulant in addition to aspirin and/or clopidogrel (e.g. warfarin, direct-acting oral anticoagulants)

Screening and enrollment: Participants will be identified prospectively, within the 2-hour period after CT scan in the ED, by research personnel that are trained and familiar with the inclusion and exclusion criteria. An additional CT scan may be performed as standard care at UPMC Presbyterian for those participants being transferred to UPMC Presbyterian after the injury is identified at an outside facility. Those subjects who arrive more than 2 hours after initial scan at the outside hospital will still be considered for enrollment. Patients who meet all inclusion and no exclusion criteria will be randomized to CSPs or standard of care based upon the predetermined randomization assignment. Patients who meet all inclusion and no exclusion criteria will be randomized to CSPs or standard of care based upon the predetermined randomization assignment.

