**Study Intervention:**

**Study Intervention Arm:** Patients randomized to the intervention arm will receive an early infusion of urgent release cold stored platelets (CSP) once the patient is determined to meet all inclusion and no exclusion criteria. When clinically feasible, patients will undergo VerifyNow Aspirin or P2Y12 testing following initial platelet transfusion. Those patients who have not increased their respective ARU or PRU measurements to levels consistent with no drug effect (ARU > 550; PRU > 220), or who have another clinical indication for additional platelet transfusion, may undergo a second CSP infusion.

CSP infusion will occur once IV access is obtained irrespective of location. CSP infusion should be initiated first when possible but can be infused concomitantly with other transfusion requirements including packed red blood cells, plasma, or whole blood per institutional standard care. The administration will be begun by clinical staff.

**Standard Care Arm:** Patients randomized to the standard care arm will receive room temperature (RT) platelet transfusion per standard care at the University of Pittsburgh once the patient meets all inclusion and no exclusion criteria. When clinically feasible, patients will undergo VerifyNow Aspirin or P2Y12 testing following initial platelet transfusion. Those patients who have not increased their respective ARU or PRU measurements to levels consistent with no drug effect (ARU > 550; PRU > 220), or who have another clinical indication for additional platelet transfusion, may undergo a second RT platelet infusion.

**Randomization and Masking:** Individual patients determined to meet all inclusion and no exclusion criteria in the emergency department will be randomized and assigned according to a 1:1 ratio to CSP infusion or standard care using a permuted block design with variable block sizes of 4 and 6. The arm assignment will be provided in real time at the individual patient level by accessing an electronic randomization system. Backup envelopes containing randomization assignments will be available by contacting the Data Coordinating Center should there be any issues or failure of the electronic randomization system. Trauma and Neurosurgical attending and ED physicians will not be masked to treatment assignment as the study intervention is a blood product and full traceability is required. Arm assignment will be concealed to all outcome assessors performing the GOSE during follow-up.

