**Platelet Hemostatic Function:** Once randomized, blood sampling for platelet hemostatic function prior to platelet transfusion irrespective of arm assignment will be performed if clinically feasible. Following each platelet transfusion, further assessment of platelet hemostatic function may be performed (up to 2 times). Platelet hemostatic function will be assessed by TEG analysis and TEG with platelet mapping. Whole blood aggregometry and flow cytometry will be performed when feasible across both arms.

**Thromboembolic events:** Pulmonary embolism, venous thrombosis, or arterial thrombosis that occurs during the primary admission hospital stay will be documented for all enrolled patients. Radiographic confirmation via CT imaging, transthoracic or trans-

esophageal echo, or ventilation/perfusion scanning will be required. Presumed or clinical suspicion for an embolic event that is unable to be verified radiographically will also be documented.

**Severity Stratification:** TBI characteristics will be recorded and based upon CT imaging results (classification: subarachnoid, subdural, intracerebral hemorrhage, epidural, +/- shift, multifocal) and TBI severity will be characterized by presenting GCS, Abbreviated Injury Severity (AIS) coding and Rotterdam CT scores.

**Predefined Subgroups:** Predefined subset analyses for the TBI cohort will be performed looking at 1) patients who did or did not receive a craniectomy/craniotomy, 2) patients who did or did not require ICP monitoring, 3) patients arrived from the scene of injury versus those brought from a referral hospital; 4) patients with a pre-injury history of aspirin use as compared to clopidogrel use; 5) CSPs with shelf time of 1 to 7 days as compared to 8 to 14 days. It is recognized that the study is not appropriately powered for these subgroup comparisons and the results and conclusions formulated from these subgroup analyses will be considered exploratory in nature and will not be used as a basis for treatment recommendations.

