A two-sided Chi-square test will be used to compare the distribution of the GOS-E between the treatment arms. An ordinal polytomous regression model will then be used to assess the independent impact of CSP on GOS-E after controlling for potential confounding effects of baseline characteristics which reveal imbalance between treatment groups. The analytic approach for the secondary trial outcomes will vary based on the type of outcome. For binary outcomes, a two-sided Chi-square test for proportions will be used to compare the proportions between those receiving and not receiving CSP. A logistics regression model will then be used to assess the independent impact of CSP on the secondary trial outcomes while adjusting for baseline GCS. For time-to-event outcomes (e.g., time to death), Kaplan-Meier curves will be generated for each treatment group and a log-rank test will be used to compare the distribution of the cumulative proportion. A Cox-proportional hazards regression model will be used to assess the independent impact of CSP on time to death after controlling for baseline GCS. For continuous outcomes a two-sided t-test for means will be used to compare the means between those receiving and not receiving CSP. An analysis of covariance model will be used to assess the independent effect of CSP. after controlling for baseline GCS .

Analyses to test for the homogeneity of the treatment effect will be carried out for the pre-defined subgroups. Regression models appropriate for the outcome variable (e.g., logistic regression for binary outcome variables) will stratified by the pre-defined subgroups. Estimate of the treatment effect (odds ratio) and 95% confidence interval will be generated for each model and displayed on a forest plot.

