Secondary analyses will be conducted to assess the impact of age of the CSP on outcomes. These analyses will be carried out among those who are randomly assigned to the CSP group and the impact of the age of the CSP on outcomes will be evaluated. Since the sample will not be randomly assigned, it will be important to adjust for potential confounding effects. A propensity score will be generated as an indicator of the age of the CSP ( $\leq 7$  days vs.  $> 7$  days). Multivariable regression models will be used to assess the independent relationship of age of the CSP on outcome. The model type will vary based on the outcome (e.g., logistic regression for binary variables). Each model will include a fixed main effect for the indicator of the age of the CSP as well as an inverse probability weight for the propensity of getting CSP  $\leq 7$  days of age.

**Sample Size Justification and Power Analysis (n=100):** For the enrollment, adherence and event rates needed for planning and feasibility analyses, we calculated the two-sided 95% CI for proportions ranging from 0.70 to 0.90. For example, a sample size of 100 produces a two-sided 95% CI of 0.82 to 0.95 when the sample proportion is 0.90. When the sample proportion is .70, the two-sided CI is 0.60 to 0.82. These confidence intervals are then repeated within the treatment arm.

Sample Size	Width	Proportion (P)	Lower Limit	Upper Limit
Full Sample				
100	0.19	0.700	0.60	0.82
100	0.17	0.800	0.71	0.87
100	0.13	0.900	0.82	0.95

One Treatment Arm				
50	0.27	0.700	0.55	0.82
50	0.24	0.800	0.66	0.90
50	0.19	0.900	0.78	0.97

For the principle secondary clinical outcome of the GOSE, based on a 2x8 (treatment x GOSE) there is 80% power to detect an effect size of 0.3788, assuming a type I error rate of 0.05, a two-sided alternative hypothesis, 7 degrees of freedom, and a sample size of 50 participants per treatment group.

**Randomization of Ineligible Participants:** It is anticipated that there will be a small proportion of patients enrolled who receive CSPs or standard care that in retrospect will not have met the entry criteria and are thus ineligible. In this circumstance, patients will be analyzed according to the group to which they were randomized. Subgroup analyses based on eligibility criteria will be performed if the number of patients so affected is large.

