## Data Management

**Data Sources:** Data will be collected prospectively as patient care progresses. This will include a review of the emergency medical patient care report(s), Emergency Department and electronic/ paper hospital records.

**Surveillance for Outcomes and Data Elements:** Data will be collected prospectively as patient care progresses. This will include a review of the medical patient care report(s), Emergency Department and electronic/ paper hospital records.

**Prehospital elements:** Mechanism of injury, prehospital vital signs including lowest GCS, lowest systolic blood pressure, highest heart rate, need for intubation/advanced airway, transported from scene, transported from referral hospital, ground transport, air medical transport.

**In-Hospital Data:** Demographics, shock severity (base deficit, lactate), injury characteristics, GCS and pupil exam, ED vitals, ED interventions (chest tubes, intubation), injury severity, operative interventions and timing of interventions, injury severity score, ICU days, ventilator days, length of stay, multiple organ dysfunction scores (daily), nosocomial infectious outcomes, blood gas results, x-ray reads, transfusion of blood and blood components, resuscitation requirements, all primary and secondary outcomes will be recorded.

**Data Entry:** The DCC will create an electronic data management system that will include a password-protected SSL website for data entry with built-in dynamic features such as data encryption, user authentication, range and data type checks, real time reports, data corrections tracking, and the capability to save and reload incomplete forms. The DCC will also draft a comprehensive data management manual that includes detailed instructions and provide training and technical assistance. Participants will be identified by a study ID only. Site will be required to store hard-copy source documentation separately in a secured, locked cabinet.

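### The GOS-E ordinal model fixes no covariates and picks them on observed imbalance, so recorded prognostic variables (age, pupils, Rotterdam CT score, even GCS) are not used by rule

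*Combined protocol and SAP*

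**What the plan says.** **What is recorded.** The Severity Stratification paragraph under Outcomes states that "TBI severity will be characterized by presenting GCS, Abbreviated Injury Severity (AIS) coding and Rotterdam CT scores". The In-Hospital Data list under Data Management opens with "Demographics, shock severity (base deficit, lactate), injury characteristics, GCS and pupil exam". Age is not named there. It is implied by demographics and by the exclusion "Age > 89 or < 18 years of age".

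**How patients are allocated.** Under Randomization and Masking, patients are "assigned according to a 1:1 ratio to CSP infusion or standard care using a permuted block design with variable block sizes of 4 and 6". No stratification factor is named.

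**How outcomes are modelled** (Statistical Analysis Plan, Analysis for Clinical Outcomes):
- GOS-E: an unadjusted two-sided chi-square test, then an ordinal regression. The regression controls for whichever baseline characteristics turn out to be imbalanced between arms. No list, test or cut-off defines imbalance.
- Binary outcomes: a chi-square test, then a logistic model estimating the effect of CSP "on the secondary trial outcomes while adjusting for baseline GCS".
- Time to death and continuous outcomes: a log-rank test or t-test, then a Cox or ANCOVA model, again with baseline GCS as the only covariate.

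**Planned power for GOS-E.** The Sample Size Justification and Power Analysis section claims that "there is 80% power to detect an effect size of 0.3788". The calculation is for the 2×8 chi-square test with 7 df, two-sided alpha 0.05 and 50 patients in each arm.

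**The concern.** Covariate adjustment in a randomised trial earns its power from variables that predict the outcome. Whether such a variable happens to be imbalanced is largely beside the point. A rule that admits covariates only after arms are compared has three weaknesses here:

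- With no threshold, two analysts could fit different GOS-E models to the same data, and the choice is made with arm-level data in view.
- Most of the time a strong predictor will look balanced and be left out, so its variation stays unexplained and the power is lost.
- GCS is fixed in the other three model types but can be absent from the model for the principal clinical outcome.

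With about 100 patients, using baseline data already collected is one of the few cheap ways to sharpen the GOS-E estimate. That estimate serves Aim 2 directly, and it feeds the choice of outcome for the larger trial under Aim 1.

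**Working it through.** **1. The plan's own figure.** The inputs are w = 0.3788, N = 100, 7 degrees of freedom and alpha 0.05. The noncentrality is N × w² = 100 × 0.3788² = 14.35. The noncentral chi-square power is 79.99%, so the stated 80% reproduces. It belongs to the unadjusted 2×8 chi-square test, and no choice of regression covariates alters it.

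**2. What each model uses by rule.**

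| Model | Fixed covariates | Can age, pupils or Rotterdam score enter? |
|---|---|---|
| GOS-E ordinal | none | only if judged imbalanced |
| Logistic | GCS | no |
| Cox | GCS | no |
| ANCOVA | GCS | no |

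**3. Size of the loss in the GOS-E model.** The documents give no prognostic strengths, so these are assumptions: proportional-odds GOS-E with 8 levels, 50 per arm, conditional treatment odds ratio 2.5, GCS log odds ratio 0.7 per SD, two-sided 0.05. Imbalance is taken as a baseline comparison with p<0.05, because the plan sets no threshold. Simulated power, 600 runs per scenario:

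| Assumed log OR per SD (age, CT score) | Imbalance rule | GCS only | GCS + age + CT |
|---|---|---|---|
| 0.7, 0.5 | 60% | 64% | 73% |
| 0.4, 0.3 | 64% | 70% | 73% |

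Gain over the planned rule: 73 − 60 = 13 points and 73 − 64 = 9 points. Gain beyond GCS alone: 73 − 64 = 9 and 73 − 70 = 3. The simulation standard error of one power figure is about √(0.73 × 0.27 / 600) = 1.8 points, and repeats differ by a few points. Fair summary ranges are roughly 8 to 14 points over the planned rule and 3 to 10 beyond GCS alone.

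**4. A second set of assumptions, with pupils included.** Conditional odds ratio 3; GCS explains 10% to 15% of latent GOS-E variance; age, pupils and Rotterdam score together explain a further 5% to 20%; two GOS-E distributions; 1000 runs each.
- Imbalance rule: 71% to 81%
- GCS only: 75% to 86%
- All four covariates: 85% to 87%

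The gain is about 5 to 15 points over the planned rule and 1 to 11 over GCS alone. The imbalance rule behaves almost like no adjustment: in one scenario with the three covariates explaining 20%, it gives 71.3%, against 71.0% unadjusted and 86.7% fully adjusted.

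**5. Rough cross-check.** If the added covariates explain a share R² of residual variance, information is multiplied by 1/(1 − R²). For R² of 5%, 10%, 15% and 20%, 100 patients are worth 105, 111, 118 and 125. A test with 80% power rises to 82.0%, 84.0%, 86.0% and 87.9%.

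**The case against.** The strongest reply is that little hangs on this. The primary outcome is feasibility, the first test for each outcome type is unadjusted, and the stated power belongs to one of those tests. That stands, and it makes this an improvement to the plan rather than a fault that threatens the trial. The 7-df chi-square ignores the ordering of GOS-E, which costs more power than the covariate choice, but that is a separate matter.

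Four stronger readings are tempting and are not supported:

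- *No outcome model can use these variables.* The GOS-E model may admit them if they look imbalanced. The defect is how they are chosen.
- *GCS is at its ceiling for many patients, so it carries little information.* The consent procedure provides for patients with GCS 15 but does not say how many there will be. No GCS distribution is given. Entry requires a significant risk of urgent neurosurgery, and the Background refers to moderate or severe TBI.
- *The Severity Stratification heading promises stratified randomisation or analysis.* Its text promises only that severity is characterised.
- *A long covariate list suits every outcome.* No event rates are given. If mortality were 10% to 20% (an assumption), 100 patients would yield 10 to 20 events. Treatment plus four covariates is five parameters, so 2 to 4 events per parameter.

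It is also fair to say that the size of the gain is assumed throughout. Under the weaker assumptions, the step from GCS alone to the fuller set is only about 3 points, with a paired simulation error of more than 1 point.

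**Conclusion.** The point holds for the GOS-E ordinal model. Its covariates are chosen after the data are seen, without a threshold and without regard to prognostic value, and GCS itself is not assured. Elsewhere GCS is the only fixed covariate, and no model is set to use age, pupils or Rotterdam score by rule.

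Under the assumptions in step 3 of the working, prespecification lifts GOS-E model power from about 60–64% to about 73%. Much of that gain comes from fixing GCS; the part due to age and CT score is about 3 to 10 points. These figures depend on the assumed prognostic strengths, the assumed odds ratio and the reading of imbalance as p<0.05. The direction does not depend on the exact values, provided the variables are prognostic. A reader might infer that the planned 80% power is wrong; it is not, since it reproduces and is untouched by this change. The improvement is desirable and confined to regression models for secondary outcomes.

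**What to change.** In Analysis for Clinical Outcomes:

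1. Delete the imbalance rule. Name a fixed set for the GOS-E ordinal model: baseline GCS, age, Rotterdam score and pupil reactivity.
2. Say which CT supplies the Rotterdam score, since transferred patients may be rescanned on arrival, and which pupil exam counts as baseline, since the data list does not time it.
3. State how missing baseline values will be handled.
4. For binary and time-to-event outcomes, extend the set only where the event count supports it, by a criterion written down before arm-level data are seen. Otherwise keep GCS alone or no covariate.

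The cost is SAP wording plus the definitions in item 2. The variables are already on the collection list, with age to be confirmed as one of the demographics. The downside is a few missing baseline values.

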Hypothesis for clinical outcomes: Early infusion of cold stored platelets as compared to standard platelet transfusion will result in improved 6 month Extended Glasgow Outcome Scale (GOS-E), lower 24 hour and in-hospital mortality, a lower need for craniotomy/craniectomy, lower need for ICP monitoring, a lower rate of TBI progression, improved hemostatic function, reversal of platelet inhibition and a similar rate of allergic/transfusion reactions and incidence of transfusion related acute lung injury in patients with TBI requiring platelet transfusion.

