In order to facilitate the early administration of platelets, randomization of eligible patients will occur within 2 hours of diagnosis of TBI via CT scan in the ED.

The study team may call the participant to check on their status after 30 days and again after 6 months. If the participant is discharged to another facility, they may be contacted at that facility for an update of their condition.

If we are unable to get in touch with the participant or with the facility they were discharged to, we will check survival status on a public access database using personal identifiers such as name, date of birth, and social security number.

**Follow-up procedures:** Galveston Orientation and Amnesia Test (GOAT): We will obtain the GOAT score prior to discharge and the calculated score per standard methods. (Figure 1) GOAT is a 10-item questionnaire used to quickly assess post-traumatic amnesia following head injury. The GOAT is read orally to the patient and may be easily administered at the bedside. The total score accounts for orientation of person, place, and time, and recollection of events pre and post- injury. Cutoff scores are available to identify abnormal, borderline, and normal orientation and it will additionally determine if a participant is able to provide continuing participation consent after the process of EFIC.

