## Outcomes

**Primary Outcome:** The primary outcome for this pilot trial will be feasibility. Secondary performance and feasibility outcomes will include the proportion of eligible patients that can be randomized, 2) the proportion of eligible patients who are enrolled in the trial, 3) proportion of enrolled patients which adherence to the study protocol, and 4) proportion of enrolled patients who complete study follow-up.

**Secondary Outcomes:** Our principle secondary clinical outcome for the proposal will be 6-month Extended Glasgow Outcome Scale (GOS-E). Additional secondary outcomes will include 24-hour mortality, in-hospital mortality, need for craniectomy/craniotomy, need for ICP monitoring, TBI progression based upon serial CT imaging in initial 24 hours, Galveston Orientation and Amnesia Test (GOAT score) at discharge, incidence of allergic/transfusion reaction, incidence of transfusion related acute lung injury (TRALI), measurements of platelet hemostatic function, and incidence of thromboembolic events.

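### Predefined subgroups 1 and 2 (craniectomy/craniotomy, ICP monitoring) are generally fixed after randomization and are outcomes CSP is meant to lower, so their stratum odds ratios cannot safely be read as treatment effects

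*Combined protocol and SAP*

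**What the plan says.** Under Predefined Subgroups (Outcomes section), the first two of five subset analyses are "1) patients who did or did not receive a craniectomy/craniotomy, 2) patients who did or did not require ICP monitoring". That paragraph adds that the study is not powered for these comparisons, that results and conclusions are exploratory, and that they will not support treatment recommendations.

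The same two variables appear under Secondary Outcomes: "Additional secondary outcomes will include 24-hour mortality, in-hospital mortality, need for craniectomy/craniotomy, need for ICP monitoring". The hypothesis for clinical outcomes in the Specific Aims expects CSP to bring "a lower need for craniotomy/craniectomy, lower need for ICP monitoring, a lower rate of TBI progression".

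On timing, patients qualify when they are "at significant risk for urgent neurosurgical procedure as determined by neurosurgical evaluation", and "randomization of eligible patients will occur within 2 hours of diagnosis of TBI via CT scan in the ED". On masking, "Trauma and Neurosurgical attending and ED physicians will not be masked to treatment assignment".

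Analysis for Clinical Outcomes plans tests of homogeneity of the treatment effect across the predefined subgroups, using models stratified by subgroup. It then says: "Estimate of the treatment effect (odds ratio) and 95% confidence interval will be generated for each model and displayed on a forest plot". No subgroup is exempted.

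**The concern.** A subgroup odds ratio is a randomized comparison only if membership could not have been changed by the assigned arm. Here the plan uses the same variable both as a possible result of treatment and as the stratifier for the treatment effect.

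Suppose CSP spares some patients a craniotomy. If the spared patients are mostly those with less severe injury among the ones who would otherwise have had surgery, the CSP patients who still have surgery are sicker on average than the operated control patients. The unoperated CSP group, having taken in the spared patients, is also sicker than the unoperated controls. Unmasked surgeons are a second route by which the arm could affect membership.

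What is at stake is the reading of the forest-plot rows for these two subgroups. Aim 1 uses this pilot to choose the population and primary outcome for a larger trial, so a row labelled as a treatment effect could be carried forward as one.

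**Working it through.** **1. Are the variables post-randomization?** The documents do not say when a craniotomy or an ICP monitor starts to count. At entry the patient is at risk of a procedure, and randomization follows within 2 hours of the CT diagnosis in the ED. Most procedures will therefore come later. Screening and enrollment also admits transferred patients whose outside scan was more than 2 hours before arrival, so an earlier procedure is not excluded. Hence generally, not always.

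**2. Is there a plan figure to reproduce?** Not for the subgroups. The only power figure, for whole-cohort GOSE (w = 0.3788, 7 df, 50 per arm), does reproduce: N = 100 gives power of 79.99%. This point does not rest on it.

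**3. Illustrative model.** All rates are assumed because the documents give none.
- Severity U is standard normal.
- P(craniotomy | U) = expit(a + bU), with a set to give 30% in controls and 27%, 22.5% or 15% under CSP (cuts of 10%, 25% and 50%).
- P(poor outcome | U) = expit(c + bU), with c set to give 40% overall.
- The slope b is 1.0 or 1.5 per SD, the same for both variables. Neither CSP nor the procedure affects the outcome.
- Within stratum s, P(poor | s) = ∫P(s | u)P(poor | u)φ(u)du / ∫P(s | u)φ(u)du. OR = odds under CSP / odds under control.

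| Cut in craniotomy | b | OR, craniotomy | OR, none | Ratio of ORs |
|---|---|---|---|---|
| none | 1.0 or 1.5 | 1.00 | 1.00 | 1.00 |
| 10% | 1.0 | 1.025 | 1.021 | 1.004 |
| 10% | 1.5 | 1.048 | 1.038 | 1.010 |
| 25% | 1.0 | 1.067 | 1.054 | 1.012 |
| 25% | 1.5 | 1.131 | 1.098 | 1.030 |
| 50% | 1.0 | 1.147 | 1.113 | 1.031 |
| 50% | 1.5 | 1.305 | 1.207 | 1.081 |

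**4. The last row in full.**
- Craniotomy: poor outcome 0.6693 (CSP) against 0.6080, so OR = (0.6693/0.3307)/(0.6080/0.3920) = 1.305.
- No craniotomy: 0.3525 against 0.3109, so OR = (0.3525/0.6475)/(0.3109/0.6891) = 1.207.
- Whole arm, CSP: 0.15 × 0.6693 + 0.85 × 0.3525 = 0.400.
- Whole arm, control: 0.30 × 0.6080 + 0.70 × 0.3109 = 0.400.

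Both strata look worse under CSP although the arms have identical outcomes overall.

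**5. Other assumed inputs.**
- Control craniotomy 20-40% and poor outcome 20-50%, with a halving: ORs 1.07-1.37, ratio 1.02-1.10.
- ICP monitoring, assumed control rate 10-50% and poor outcome 40%: ORs 1.01-1.07, 1.02-1.18 and 1.04-1.43 for the three cuts, ratio 1.00-1.09.
- Adjusting for a GCS-like covariate correlated 0.5 or 0.7 with severity moves 1.305/1.207 to about 1.25/1.17 or 1.19/1.13. The bias shrinks but remains.
- A different mechanism: 30% craniotomy in both arms, but slope 1.0 under CSP against 1.5 in controls. The ORs become 0.81 and 1.10, so direction depends on mechanism.

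**6. Precision.** For the last table row, expected craniotomy-stratum counts at 50 per arm are 7.5 (CSP) and 15 (control). The variance of the log OR is 1/5.02 + 1/2.48 + 1/9.12 + 1/5.88 = 0.88, so the 95% CI factor is exp(1.96 × √0.88) ≈ 6.3. Across the base cases the factors are about 4.2-6.3 (craniotomy), 2.5-2.8 (none) and 5.7-8.0 (ratio of ORs).

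**The case against.** The strongest reply is that the plan has already contained the harm. These analyses are declared underpowered and exploratory and are barred from supporting treatment recommendations, and the shifts above sit well inside the confidence intervals. That stands, and it keeps the point minor. But the caveat is about power. More patients would narrow the interval around a value that still is not the treatment effect.

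A second reply is that the ratio of the two odds ratios barely moves in the main model, so the homogeneity test could stay. The arithmetic is right for that model, but a contrast between strata that treatment may have reshaped is not a clean test of effect modification, and the unequal-slope scenario shows that it can move.

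A third is that adjustment for baseline GCS would deal with it. The SAP specifies that adjustment for several main secondary analyses but does not state it for the subgroup models, and the calculation shows only partial relief.

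Stronger readings are tempting but unsupported:
- A reader might infer that these rows will be biased toward harm under the trial's own hypothesis. The documents do not support this. The hypothesis also includes better GOSE and lower mortality, whereas the model sets the outcome effect to zero. The shared upward shift belongs to that model.
- A reader might take the Non-adherence paragraph as proof that surgery follows randomization. It shows only that the plan anticipates urgent neurosurgery in some patients assigned to CSP who then do not receive it although it is available. It gives no timing.

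**Conclusion.** The point holds, conditionally, as a minor one. Craniectomy/craniotomy and ICP monitoring are secondary outcomes that CSP is hypothesised to lower, yet the plan also uses them to define strata for a treatment odds ratio. If CSP or unmasked knowledge of the arm alters who has these procedures, the odds ratio in that stratum cannot be read as the CSP effect. If neither does, this bias is absent.

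Size and direction cannot be derived from the documents. The base-case range of 1.02 to 1.31 rests on the assumed 30% craniotomy rate, 40% poor outcome, common severity slope and null outcome effect. With 50 per arm, such shifts could not be told from chance.

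Nothing here reaches the feasibility primary outcome, the whole-cohort GOSE comparison or the 24-hour mortality analyses, none of which uses these strata. Subgroups 3 and 4 (origin of transport, pre-injury drug) are baseline factors and are not in question.

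**What to change.** Analyse craniectomy/craniotomy and ICP monitoring only as outcomes, and drop them from the treatment-effect subgroup models, the homogeneity tests and the forest plot. If the sponsor wants to keep the strata, report them as descriptive and state that between-arm differences within them are not causal because membership may be affected by the arm.

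Optionally, if the aim was to look at severity, use a baseline measure. The protocol already says "TBI severity will be characterized by presenting GCS, Abbreviated Injury Severity (AIS) coding and Rotterdam CT scores". Presenting GCS can be used directly. A Rotterdam score should come from a named scan done before randomization, because the text does not say which scan supplies it and serial CT is planned over the first 24 hours.

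The cost is a short amendment to Predefined Subgroups and Analysis for Clinical Outcomes, with the prospective IRB approval that Protocol Compliance requires, and the loss of two exploratory subgroup comparisons. No new data are needed: presenting GCS is recorded, and a CT showing the injury is a condition of entry.
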